### 6.2.1.2 Capecitabine

Local label should be used for capecitabine dose modifications for the management of adverse reactions or as described in Table 6-7.

Toxicity*	During a course of therapy	Dose adjustment for next treatment (% of starting dose)
Grade 1	Maintain dose level.	Maintain dose level.
Grade 2		·
1 st appearance		100%
2 nd appearance	Interrupt until resolved to grade 0-1.	75%
3 rd appearance		50%
4 th appearance	Discontinue treatment permanently.	-
Grade 3		 
1 st appearance		75%
2 nd appearance	Interrupt until resolved to grade 0-1.	50%
3 rd appearance	Discontinue permanently.	-
Grade 4		·
1 st appearance	Discontinue permanently OR If physician deems it to be in the patient's best interest to continue, interrupt until resolved to grade 0-1.	50%

## 6.2.1.2.1 Adjustment of Starting Dose in Special Populations

### **Renal Impairment**

No adjustment to the starting dose of capecitabine is recommended in patients with mild renal impairment (creatinine clearance = 51 to 80 mL/min [Cockroft and Gault, as shown below]). Dose reduction should be made if grade 2 to 4 adverse events occurred, Table 6-7.

Cockroft and Gault Equation:

Creatinine clearance for females =  $0.85 \times \text{male value}$ 

## **Elderly**

For capecitabine monotherapy, no adjustment in starting dose is needed. However, sever Grade 3 or 4 treatment-related adverse events were more frequent in patients ≥ 60 years old compared to younger patients. Careful monitoring of elderly patients is advisable.

### **Hepatic Impairment due to Liver metastasis**

Patients with mild or moderate hepatic impairment due to liver metastasis should be monitored carefully while administered capecitabine. No starting dose reduction is necessary.

### 6.2.1.3 Exemestane

The most frequently reported adverse effects for exemestane are gastrointestinal disturbances, hot flushes, arthralgia, myalgia, sweating, fatigue, and dizziness. Other reported effects include headache, insomnia, somnolence, depression, skin rashes, alopecia, asthenia, and peripheral and leg edema. Thrombocytopenia and leucopenia have been reported occasionally. Reductions in bone mineral density can occur with long-term use of exemestane.

Exemestane was generally well tolerated, and adverse events were usually mild to moderate. Adverse events occurring in greater than 10% of patients include hot flushes (14%), nausea (11.9%), insomnia, headache, increased sweating, joint and musculoskeletal pain, and fatigue (USPI; Aromasin SmPC August 2008 (UK as RMS for EU MRP)). Androgenic effects were reported in a limited number of patients (4.3%) (Buzdar 2003).

Refer to the package insert of the local supply of exemestane for more details.

### 6.2.2 Follow-up for toxicities

Patients whose treatment is interrupted or permanently discontinued due to an adverse event or abnormal laboratory value must be followed at least once a week for 4 weeks, and subsequently at 4-week intervals, until resolution or stabilization of the event. All patients will be followed for onset of any new serious adverse events for 30 days following the last dose of study treatment.

### 6.3 Concomitant medications

All medications and non-drug therapies taken within 30 days prior to starting study treatment should be reported on the Concomitant Medication/Significant Non-drug Therapy eCRF. The investigator should instruct the patient to notify the study site about any new medications (including over-the-counter drugs and herbal/alternative medications) he/she takes after the start of study treatment. Patients must be instructed not to take any additional medications (including over-the-counter products and herbal/alternative medications) during the trial without prior consultation with the investigator. All medications (other than study treatments) and significant non-drug therapies (including physical therapy and blood transfusions) administered after the patient starts study treatment must be listed on the Concomitant medications/Significant non-drug therapy eCRF.

## 6.3.1 Prohibited concomitant therapy and concomitant therapy requiring caution and/or action

The following concomitant treatments are not allowed during the study:

- Investigational or commercial anticancer agents, such as chemotherapy, immunotherapy, targeted therapy, biological response modifiers, or endocrine therapy other than exemestane (including steroids) should not be given to patients.
- Hormone replacement therapy, topical estrogens (including any intra-vaginal preparations), megestrol acetate and selective estrogen-receptor modulators (e.g. raloxifene) are prohibited.

- Prolonged systemic corticosteroid treatment, except for topical applications (e.g. rash), inhaled sprays (e.g. obstructive airways diseases), eye drops or local injections (e.g. intraarticular) should not be given. A short duration (<2 weeks) of systemic corticosteroids is allowed (e.g. chronic obstructive pulmonary disease, anti-emetic).
- Hematopoietic growth factors (e.g. erythropoietins, G-CSF and GM-CSF) are not to be administered prophylactically. Use of these should be reserved to cases of severe neutropenia and anemia as per the labeling of these agents.
- Oral coumarin-derivate anticoagulants such as warfarin and phenprocoumon should be avoided in patients receiving capecitabine as study treatment. If patient needs to take coumarin-derivate anticoagulants anticoagulant response (INR or protrombin time) should be monitored frequently in order to adjust the anticoagulant dose based on Xeloda prescribing information. Altered coagulation parameters and / or bleeding, including deaths have been reported during concomitant use.
- Aluminium hydroxide- and magnesium hydroxide-containing antacid (such as Maalox) should not be administrated immediately after capecitabine because of their effect on the pharmacokinetics of capecitabine.

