#### **Amendment 1**

#### **Amendment rationale**

At the time of this amendment, 07-Jun-2013, 4 patients were randomized, 6 patients were in screening and 1 subject was discontinued due to disease progression.

The rationale of this amendment is as follows:

- Significant drug-drug interaction between sorivudine and 5-FU leads to increased fluoropyrimidine toxicity, which is potentially fatal (EU SmPC for Xeloda®). Sorivudine pertains to a class of antiviral drugs for the treatment of Herpes simplex infection. Therefore, capecitabine must not be administered concomitantly with sorivudine or its chemically related analogues, such as brivudine (EU SmPC for Xeloda®). Accordingly, a new exclusion criteria (re-numbered as #19) was added to exclude subjects who are being treated with sorivudine or its chemically related analogues (e.g. brivudine) or to have at least 4 weeks period between end of treatment with such drugs and randomization date.
- Altered coagulation parameters and/or bleeding have been reported in patients taking capecitabine concomitantly with coumarin-derivative anticoagulants such as warfarin and phenprocoumon. These events occurred within several days and up to several months after initiating capecitabine therapy in patients with and without liver metastases (EU SmPC and US PI for Xeloda®). Therefore, to be consistent with exclusion criterion #20 (renumbered as #18 after amendment), which excludes patients under coumarin-derivate anticoagulants, the exclusion criterion #15 was updated to also exclude patients under low dose warfarin treatment.

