#### Changes to the protocol

Changes to specific sections of the protocol are shown in the track changes version of the protocol using strike through red font for deletions and red underlined for insertions.

The changes to the protocol are as follows:

- 1. List of abbreviations: Typographic corrections
- 2. Sections 1.1.1, 1.2.3 and 2.5.2: Typographic corrections
- 3. Section 4.1.1: Wording for capecitabine and exemestane central supply where applicable was added. Clarification for monitoring patients with hepatitis C positive at baseline was made.
- 4. Sections 4.1.2 and 7.2.1.1: The wording for additional confirmatory scan after initial observation of tumor response was updated for clarity
- 5. Section 5.2:
  - a. Inclusion criterion #4 was updated to specify that recurrence or progression should occur while on or after adjuvant treatment with letrozole or anastrozole, instead of aromatase inhibitors in general, for clarity
  - b. To insure adequate renal function at study entry, creatinine clearance > 60 ml/min was added to inclusion criterion #9
- 6. Section 5.3:
  - a. Wording "low dose warfarin" was removed from the exception scenarios in exclusion criterion #15
  - b. "e.g." was added before the list of CYP3A modifiers in exclusion criterion #17 to clarify these drugs as examples
  - c. Exclusion criteria #18 and #19 were removed
  - d. A new exclusion criterion numbered as 19 was added
- 7. Sections 6.1.1 and 6.1.2: Wording for local supply of commercially available exemestane and capecitabine was removed and a note for central supply of these drugs where applicable was added
- 8. Section 6.3.1:
  - a. A note was added on bisphosphonate therapy, which is not allowed during the study for chronic prevention of bone metastases
  - b. Section 6.3.1.1: This section was reworded for clarity, and a note was added for guidance on the classification of P-glycoprotein modifiers if not found in the table 6-9. Tables 6-8 and 6-9 were updated according to the most recent references available.
- 9. Table 7-1: The word "visit" under "Treatments" for clarity and missing word "twice" for capecitabine dosing were added

- 10. Section 7.1.1.2 and 7.1.1.3: Wording on screen failure definition was updated for clarity, and randomization was added to replace first drug treatment
- 11. Section 7.1.2: Clarification was made to include an initial dosing window upon randomization
- 12. Section 7.2.1.1: Lost to follow up was added for clarity
- 13. Section 7.2.2:

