- 10. Currently receiving any hormone replacement therapy, unless discontinued prior to randomization.
- 11. Current or history of CNS metastases. Patients with symptoms suggestive of CNS metastases should have a CT/MRI to rule out CNS metastasis prior to randomization to be eligible.
- 12. Patients receiving concomitant immunosuppressive agents or chronic corticosteroids use at the time of study entry except topical applications, inhaled sprays, eye drops or local injections.
- 13. Bilateral diffuse lymphangitic carcinomatosis
- 14. Patients with a known history of HIV seropositivity. Screening for HIV infection at baseline is not required.
- 15. Active, bleeding diathesis, or on oral anti-vitamin K medication (except LMWH and acetylsalicylic acid or equivalent, as long as the INR is ≤2).
- 16. Any severe and / or uncontrolled medical conditions.
- 17. Patients being treated with drugs recognized as being strong inhibitors or inducers of the isoenzyme CYP3A (e.g.\_Rifabutin, Rifampicin, Clarithromycin, Ketoconazole, Itraconazole, Voriconazole, Ritonavir, Telithromycin) continuously for at least 7 days during any time period in the last 2 weeks prior to randomization
- 18. Patients being treated with coumarin-derivate anticoagulants such as warfarin and phenprocoumon
- 19. Patients under treatment with sorivudine or its chemically related analogues, such as brivudine, or those who discontinue this treatment less than 4 weeks prior to randomization
- 20. History of noncompliance to medical regimens
- 21. Patients unwilling to or unable to comply with the protocol

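### Protocol Section 6.3.1 does not carry into treatment the sorivudine/brivudine restriction that the protocol states for capecitabine and applies only at entry

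*Protocol*

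**What the plan says.** Three parts of the protocol bear on these drugs.

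- **Amendment 1, rationale.** The first reason given for the amendment is: "Significant drug-drug interaction between sorivudine and 5-FU leads to increased fluoropyrimidine toxicity, which is potentially fatal (EU SmPC for Xeloda"). It goes on to state that "capecitabine must not be administered concomitantly with sorivudine or its chemically related analogues", brivudine being the named example of an analogue. The EU SmPC is the only source cited for either statement.
- **Section 5.3, exclusion criterion 19 (repeated in the protocol summary).** It excludes "Patients under treatment with sorivudine or its chemically related analogues, such as brivudine, or those who discontinue this treatment less than 4 weeks" before randomization. The amendment's list of changes records this as "A new exclusion criterion numbered as 19 was added".
- **Section 6.3.1.** The list is headed "The following concomitant treatments are not allowed during the study". It has six bullets: anticancer agents, hormonal agents, prolonged systemic corticosteroids, prophylactic growth factors, coumarins, and aluminium/magnesium antacids. The coumarin bullet is specific to one arm: "Oral coumarin-derivate anticoagulants such as warfarin and phenprocoumon should be avoided in patients receiving capecitabine as study treatment". The notes under the list cover bisphosphonates and denosumab, local radiotherapy, vaccines and phenytoin. Section 6.3.1.1 and Tables 6-8 and 6-9 cover CYP3A4, CYP2C9 and P-glycoprotein.

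Two general provisions also apply. Section 6.3 tells patients to consult the investigator before taking anything new. Sections 4.2 and 6.1.1 tie capecitabine treatment to its local label.

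**The concern.** The reason given for criterion 19 concerns treatment. Two drugs interact when they are taken together, and no patient takes study capecitabine before randomization. An entry criterion with a four-week look-back removes patients who already use these antivirals or stopped them recently. It says nothing about a patient who is prescribed one later, while on capecitabine.

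The place where a site would check such a prescription is Section 6.3.1, and a site that reads it as written finds no restriction on a combination that the protocol rules out elsewhere. At stake is patient safety in the capecitabine arm, which is the comparator in the key secondary objective. To a lesser degree, the reading of severe toxicity in that arm is also affected.

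**Working it through.** No calculation applies: the point rests on no event count, effect size or precision figure. The check is a side-by-side reading.

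**1. Where the drugs are named.** They appear in the Amendment 1 rationale, in exclusion criterion 19 and in the protocol summary's copy of that criterion. Sections 6.3, 6.3.1 and 6.3.1.1, Tables 6-8 and 6-9, and SAP Sections 2.4.1 and 3.7 do not name them.

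**2. How other capecitabine interactions are treated in the current text.**

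| Drug or class | Entry rule (Section 5.3) | On-treatment text |
|---|---|---|
| Sorivudine, brivudine | Criterion 19 | None |
| Coumarins | Criterion 18 | Section 6.3.1, list |
| Aluminium/magnesium antacids | None | Section 6.3.1, list |
| Phenytoin | None specific to capecitabine | Section 6.3.1, notes |
| CYP2C9 substrates | None | Section 6.3.1.1 |

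The omission is therefore not a drafting convention under which capecitabine interactions are left to the label or to the eligibility criteria. Coumarins were handled in the same amendment and sit in both places. Three other interactions are named for the treatment period without a capecitabine-specific entry criterion. The interaction that the protocol describes as potentially fatal is the only one in the table without on-treatment text.

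**3. Whether this merely compares an amendment log with later text.** It does not. The rationale is used only as the stated reason for criterion 19, which is in force. The gap lies between Sections 5.3 and 6.3.1 of the current protocol. The change lists show how it arose. Amendment 1 answered the interaction with an exclusion criterion, while its changes to Section 6.3.1 concerned bisphosphonates and the CYP/P-glycoprotein material. Amendment 2 returned to the section for denosumab and CYP2C9 substrates.

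**4. How far the general provisions reach.** Consultation brings the prescription to the investigator but names no drug, so it works only if the investigator already knows the interaction or finds it outside Section 6.3.1. The label provision works where the local label carries the restriction. For coumarins the rationale cites both the EU SmPC and the US PI. For sorivudine it cites the EU SmPC alone, so the documents do not show that every local label covers it.

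**5. Who is affected.** The plan allocates 300/3 = 100 patients to capecitabine. Amendment 3 reports 309 recruited in total, without arm counts, and 11 still on treatment across all three arms.

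**The case against.** The strongest reply is that nothing in the protocol permits the combination. The rationale forbids it in a document that investigators hold, criterion 19 puts the drug class in front of every site, new medicines go through the investigator, and capecitabine follows its label. On this view one list is incomplete, and no two rules conflict. Most of this is right. A reader might infer that the protocol allows these drugs on treatment, or that the label is the only protection; the documents support neither. What remains is that the cover is indirect, and that the section written to list on-treatment restrictions omits one the protocol itself states.

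Three further inferences are tempting and should not be drawn.

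- **That a co-prescription would leave no trace.** Protocol Section 6.3 requires every medication after treatment start to be recorded, Section 9.3 has them coded, and Protocol Section 10.3.2 and SAP Section 3.7 list and summarize them by ATC class, preferred term and arm. A brivudine record would be visible. All that is lacking is a targeted look.
- **That SAP Section 2.4.1 is at fault.** It deals with CYP3A and P-glycoprotein, with a CYP2C9 caution, and the protocol does not describe the sorivudine interaction in those terms. A change before database lock is in any case no longer possible, since SAP Addendum 1 is dated after it.
- **That an expected number of cases can be given.** The documents contain no rate of herpes treatment and no share of it using these drugs. Any count would rest on assumptions alone and would measure treated episodes, not exposure to sorivudine or brivudine.

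**Conclusion.** The inconsistency is real and the textual reading is secure. The protocol states that capecitabine and these drugs must not be combined, acts on this only at entry, and leaves them out of the on-treatment section that names four other capecitabine interactions.

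The consequence is much less certain. Whether any patient was exposed is unknown, and the residual risk depends on local labels that the documents do not reproduce. The protocol calls the interaction potentially fatal, so the case rests on the gravity of the possible outcome and the ease of correction, not on frequency.

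Neither the primary nor the key secondary hazard ratio, nor its precision, is affected. With 11 patients on treatment across all arms at Amendment 3, the prospective benefit of a correction at that point was small. The omission applied, however, to on-treatment use under the amended text from Amendment 1 onward, when 4 patients had been randomized.

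**What to change.** The Amendment 1 rationale, exclusion criterion 19 and Section 6.3.1 must be reconciled for patients receiving capecitabine, so that a site reading any one of them learns the same thing, and sites should be notified. The wording of the on-treatment rule is for the sponsor and its clinical advisers; none is proposed here. The cost is a short text change through the written amendment that Section 12.1 requires, plus a notification to sites. The statistical design does not change.

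Optionally, when severe toxicity in the capecitabine arm is interpreted, search the coded concomitant medications in that arm for sorivudine, brivudine and related analogues. The data are already collected and coded, so this is one descriptive search. It should be reported as done after database lock.

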### It is to be noted that:

- Use of bisphosphonate or denosumab for osteoporosis and management of bone metastases are allowed for approved indications as per local label. Chronic concomitant bisphosphonate therapy for the prevention of bone metastases are not permitted during the study. Please refer to prescribing information for details of administration. If bisphosphonate therapy is initiated after randomization, the reason for its use must be clearly documented.
- Local radiotherapy for analgesic purposes or for lytic lesions at risk of fracture may be carried out if required. Whenever possible, these patients should have a tumor assessment of the lesion(s) before they actually receive the radiotherapy. No dose modification of study treatment is needed during radiotherapy.
- Everolimus may affect the response to vaccinations making it less effective. Live vaccines should be avoided while a patient is treated with everolimus.
- The level of phenytoin should be carefully monitored in patients receiving capecitabine and phenytoin dose may need to be reduced based on Xeloda prescribing information.

## 6.3.1.1 CYP3A4, CYP2C9 and P-glycoprotein inhibitors/inducers/substrates

Everolimus is metabolized by CYP3A4 in the liver and to some extent in the intestinal wall. Capecitabine and its metabolites do not inhibit the metabolism of CYP3A4 substrates but capecitabine and/or its metabolites may inhibit the metabolism of CYP2C9 substrates.

#### Therefore:

- Co-administration of CYP2C9 substrates (e.g. Irbesartan, Losartan, Phenytoin, Cyclophosphamide) should be exercised with caution and monitored closely per capecitabine local label.
- Co-administration with strong inhibitors of CYP3A4 (e.g., ketoconazole, itraconazole, ritonavir) or should be avoided.

- Co-administration with moderate CYP3A4 inhibitors (e.g., erythromycin, fluconazole) or PgP inhibitors should be used with caution.
- Seville orange, star fruit, grapefruit and their juices affect CYP3A4 and PgP activity.
   Concomitant use should be avoided.
- Avoid the use of strong CYP3A4 inducers such as phenytoin, carbamazepine, rifampin, rifabutin, phenobarbital, St. John's wort), Please refer to Table 6-8 listing relevant inducers and inhibitors of CYP3A and to Table 6-9 for a list of relevant substrates, inducers, and inhibitors of PgP.

**Note**: Most of PgP inhibitors/inducers are also inhibitors/inducers of CYP3A4. In case the drug is not listed on Table 6-9 below, refer to the list of CYP3A modifiers (Table 6-8) and apply the same classification specified therein to the concerned PgP inhibitor/inducer. In the rare case the PgP inhibitor/inducer cannot be found in either Table 6-8 or Table 6-9, then consider the drug as a strong PgP inhibitor and follow the guidance as per the stated above.

## Table 6-8 Clinically relevant drug interactions: inducers and inhibitors of isoenzyme CYP3A

### **Inducers**

#### Strong inducers:

avasimibe, carbamazepine, phenobarbital, phenytoin, rifabutin, rifampin (rifampicin), St. John's wort (*Hypericum perforatum*)

### Moderate inducers:

bosentan, efavirenz, etravirine, genistein, modafinil, nafcillin, ritonavir, talviraline, thioridazine, tipranavir

### **Inhibitors**

### Strong inhibitors:

boceprevir, clarithromycin, cobicistat, conivaptan, elvitegravir, indinavir, itraconazole, ketoconazole, lopinavir, mibefradil, nefazodone, nelfinavir, posaconazole (Krishna et al 2009), ritonavir, saquinavir, saquinavir, telaprevir, telithromycin, tipranavir, troleandamycin, voriconazole

#### Moderate inhibitors:

amprenavir, aprepitant, atazanavir, casopitant, cimetidine, ciprofloxacin, cyclosporine, darunavir, diltiazem, dronedarone, erythromycin, fluconazole, fosamprenavir, grapefruit juice (*Citrus parasidi* fruit juice), imatinib, *Schisandra sphenanthera*, tofisopam, verapamil

Reference: Internal Clinical Pharmacology Drug-drug interaction (DDI) memo, updated Oct 2, 2011, which summarizes DDI data from three sources including the FDA's "Guidance for Industry, Drug Interaction Studies", the University of Washington's Drug Interaction Database, and Indiana University School of Medicine's Drug Interaction Table.

